Cases of tooth decay become more complex, and children are more likely to be referred into this system when the decay is severe or affects multiple teeth, the child suffers from dental anxiety, or the child is very young. Currently, General Dental Practitioners (GDPs, which we will refer to as High Street Dentists when describing a dentist who refers from their practice into the referral system) who feel unable to treat such complex cases may refer them on to a Specialist Paediatric Dentistry pathway, where they may be treated within one of two specialist settings: (Setting 1) to hospital (secondary care) or (Setting 2) to dentists with enhanced skills and specialist equipment and facilities (Community Dental Service) (7).

One solution to this crisis of children waiting, often in pain, for treatment is to increase capacity, however there are limits on being able to increase capacity within the existing specialised pathways, both within the hospital services and within the Community Dental Services. Hospital services have downward pressure from other paediatric specialties who also require specialised space and staff, and the Community Dental Service is intended to provide complex care for adults and children with additional needs, but is currently overwhelmed by otherwise healthy young children with extensive decay.

In late 2020, as a response to the increased pressure caused by Covid-19, a new model of enhanced primary care was piloted in Greater Manchester (GM), the Child Friendly Dental Practice (CFDP) Scheme. The aim was to provide timely access to dentists who have an interest in treating young children and who have received some additional training, access to a specialist-led peer support network and additional funding. The CFDPs have been developed around a prevention focused and evidence-based model of care with the aim of improving oral health outcomes. These include clinical techniques for treatment which are not typically used by High Street Dentists such as applying Silver Diamine Fluoride and placing preformed metal crowns using the 'Hall Technique' (8).

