Before Covid-19 children in Greater Manchester were already experiencing waiting times of up to 12 months for dental treatment under GA, often leading to episodes of pain, time off school and repeat courses of antibiotics. According to the Commissioners within GM as of December 2021, there were 1779 children on the waiting list, 716 of whom have been waiting over 52 weeks. These figures show the continued pressure on the system with children waiting an unacceptably long time for treatment. These numbers are now decreasing with the implementation of CFDP, where this pathway is able to take new patients entering the referral system. The CFDPs have shown promising preliminary results with 50% of children seen within a CFDP. The dental commissioning team in GM are committed to increasing the number of CFDPs by reallocating existing funding. There is considerable interest in this type of scheme from other areas of the country in view of the national policy drivers supporting flexible commissioning; following the work in GM further regional pilots have been established this year (for a minimum of 6 months) in the South East of England lead by [name] (who has agreed to join our steering committee if the study is funded – further information is available in the letter of support from [name]). There has also been interest in our research proposal from Northern Ireland and Wales.

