While the pilot indicated promising results, with 50% of children being able to be seen within a CFDP, the long term impacts and health outcomes of the use of CFDP are unknown. There have also been concerns raised from some within the field that children treated within a CFDP may still require future intervention in a more specialist service, within a short period of time. If so, there would not be a reduction on the pressure seen on these services and the overall costs of this scheme would be higher than usual care. The proposed research is required to provide a robust, longitudinal evaluation of the CFDP pathway, building on the initial work from the pilots, which can strengthen the case for nationwide adoption if shown to be successful. Following a realist evaluation approach will also mean the research will provide evidence of what works, for whom and when. The project will provide evidence of long term outcomes (treatment required, pain, use of antibiotics) and a health economic evaluation which can be utilised by commissioners for future schemes. If a high proportion of children referred to specialist services can be treated at CFDPs, this model has the potential to improve access to care across the system. In particular, increased use of CFDPs could allow hospital/specialist services to focus on those in greater need. The implementation of an alternative pathway could allow those urgent cases, and cases for which a dental GA is unavoidable, such as medically compromised children and those with additional needs, to be seen sooner. It may also reduce the need for GA for some children if they are seen sooner than they would otherwise be seen along a traditional pathway.

Research objectives.

The aim of this research is to determine the performance of CFDP pathway compared to a traditional Specialist Paediatric Dental pathway on the longer term oral health and treatment outcomes for children referred to specialist care due to severe decay and the associated health economic costs.

Our primary and secondary research questions (and subsequent objectives/methods) are as follows:

Primary

- *Does treatment through a CFDP reduce treatment under General Anaesthetic when compared to the traditional pathway over a period of 2 years?*
 - Using GA data gained from Hospital Episode Statistics (HES)/Community Dental Service (CDS) records the team will assess the number of GAs carried out along each pathway for dental extraction.

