Primary: The primary outcome, measures whether a child has had a dental extraction under General Anaesthetic two years after referral as indicated in electronic patient records (recorded through HES data or through CDS patient records).

Secondary: The secondary outcomes to be considered in this project include:

- Waiting time until first appointment
- Number of sessions of treatment
- Whether a child was successfully seen and treated. For this outcome success is defined as treatment completed by a dentist that results in a child being referred back to their own dentist or discharged, pain free.
- The number of extractions and restorations as reported in NHS BSA data
- The courses of antibiotics taken during wait and treatment
- Participants referred back into the specialist pathway within two years of referral.
- Dental pain experienced by a child
- Participants views of their treatment and engagement with the dental profession (follow up of dental appointment) as indicated by the responses to the text message. Questions will include an adapted version of the NHS Friends and Family Test, questions on satisfaction, possible negative/adverse experiences, possible positive experiences, and an option for free text comments at the end of the survey.

Qualitative work will focus on two groups: (a) dental professionals (incl. triage, in-practice dental teams, CDS teams and referring practices) and (b) patients (incl. parents and children) accessing and using CFDPs.

(a) Dental teams' attitudes and beliefs regarding CFDP will be examined to better understand what worked well, what created barriers and look at how best to support implementation for such initiatives if they become routine practice.

In a qualitative approach, we will explore dental team beliefs, attitudes, and opinions regarding CFDPs and traditional pathways. To allow for the realist evaluation to take place, a combination of focus groups and one-to-one interviews will take place with the triage team and staff at CFDPs.

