Summary descriptive data will be reported by study arm and overall using tables of frequencies or means and standard deviations as appropriate to characterise the population and identify any imbalance between groups. The comparison of outcomes from the traditional specialist dental service route (control) compared to the intervention treatment under the alternative Child-Friendly Dental Practice will be assessed to determine if there are clinically meaningful and statistically significant differences in key outcomes. The primary outcome is receipt of GA for tooth extraction within two years of initial referral. Referral along both pathways may still result in the need for a GA for some children but a key metric will be to determine whether there

is a meaningful difference in the number of GAs per referral pathway. The primary outcome will be analysed using a mixed effects logistic regression model, accounting for the traditional specialist dental service route or alternative Child-Friendly Dental Practice, with random effects for centre. An adjusted logistic regression analysis additionally accounting for the age, deprivation, ethnicity, sex of the child along with the number of teeth requiring treatment at initial examination (through the CFDP or CDS) will also be undertaken. The analysis dataset will include all participants for whom there is follow-up data from the NHS BSA and the baseline covariates.

Analysis of secondary outcomes will be undertaken in a similar manner using covariate adjusted linear or logistic regression models as appropriate, we will include the modifying effect of deprivation

The health economics analysis will adopt a cost-consequences approach whereby the costs of each pathway will be presented separately but alongside relevant outcomes: 1) dental extractions under GA, 2) count of children who are successfully seen and treated in each pathway, 3) count of treatments performed (extractions, restorations), 4) mean wait time and 5) dental pain experienced by a child. Resource use and costs from the CFDP pathway will also be used in a budget impact analysis. Differences in outcomes will be generated from the quantitative analysis.

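### Return to the specialist pathway within two years of referral works as a whole-pathway count, but it cannot compare how durable treatment is when the arms wait for different lengths of time

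*Protocol*

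**What the plan says.** The outcomes section of the protocol lists "Participants referred back into the specialist pathway within two years of referral" among the secondary outcomes. The clock starts at referral. No section restarts it at first appointment, treatment or discharge.

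Section X (Data analyses) states: "Analysis of secondary outcomes will be undertaken in a similar manner using covariate adjusted linear or logistic regression models as appropriate". The adjusted primary model to which this refers is described as "additionally accounting for the age, deprivation, ethnicity, sex of the child along with the number of teeth requiring treatment at initial examination". Waiting time and follow-up after treatment are not among the covariates, and no offset or time-to-event model is named.

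The rationale explains why returns matter. Some in the field fear that "children treated within a CFDP may still require future intervention in a more specialist service, within a short period of time", in which case pressure on specialist services would not fall and the scheme would cost more than usual care.

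On waits, the Background says of the scheme: "The aim was to provide timely access to dentists who have an interest in treating young children". The rationale suggests that some children may avoid a general anaesthetic (GA) "if they are seen sooner than they would otherwise be seen along a traditional pathway". It cites "waiting times of up to 12 months for dental treatment under GA" before Covid-19 and, for December 2021, "there were 1779 children on the waiting list, 716 of whom have been waiting over 52 weeks". Waiting time to first appointment is itself a secondary outcome.

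**The concern.** A child who is still waiting cannot yet be referred back. The wait therefore uses up part of the two-year window without offering any chance of an event. If one arm waits longer, it has less post-treatment time in which a return can be counted. A plain proportion then mixes two things: how long treatment lasts and how soon it began. The faster pathway would look less durable partly because it was faster.

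The event itself also differs by arm. The Background treats CDS and hospital as the two settings of the specialist pathway. A CFDP child sent on to CDS during the index episode enters that pathway and can be counted. A CDS child sent on to hospital never left it and cannot be. This pushes in the same direction.

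The stake is interpretation. A higher return proportion in CFDP could be read as confirming the worry about early specialist re-treatment when durability is the same.

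**Working it through.** **The plan's own figures.** This outcome has no stated rate, effect size or sample size. The protocol's 354 per group belongs to the primary GA outcome (25% v 15%, 90% power, two-sided 0.05). It reproduces with a continuity correction (335 without) and is not in dispute.

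**Inputs from the protocol.** The window is 24 months from referral, and the model has no time-at-risk term. The waiting-list figure is 716/1779 = 40% over 52 weeks. It is not used as a CDS wait below, because the surrounding text concerns treatment under GA.

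**Assumptions (not in the documents).** CFDP wait 2 months; index treatment 2 months in both arms; CDS wait 3, 6, 9 or 12 months; the same return pattern after treatment in both arms. Here a return is counted only after the index episode has ended.

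**Time at risk** = 24 − wait − 2. For CFDP this is 24 − 2 − 2 = 20 months. For CDS it is 19, 16, 13 or 10 months.

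**Pattern A, constant hazard.** h = −ln(0.8) per year, i.e. 20% return per year. Observed proportion = 1 − exp(−h × months/12).

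**Pattern B, mostly early returns.** 25% eventually return, with a median of 3 months after discharge. Observed proportion = 0.25 × (1 − 2^(−months/3)).

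| Arm (wait) | Months at risk | A: observed | A: gap from CFDP | B: observed | B: gap from CFDP |
|---|---|---|---|---|---|
| CFDP (2) | 20 | 31.1% | – | 24.8% | – |
| CDS (3) | 19 | 29.8% | 1.3 points | 24.7% | 0.1 |
| CDS (6) | 16 | 25.7% | 5.3 | 24.4% | 0.4 |
| CDS (9) | 13 | 21.5% | 9.6 | 23.8% | 1.0 |
| CDS (12) | 10 | 17.0% | 14.1 | 22.5% | 2.2 |

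Gaps are taken from unrounded values. True durability is equal in every row, so each gap comes only from the window.

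**A second set of assumptions.** Waits of 3 v 12 months, no treatment time, constant hazard with a 25% risk over 24 months: CFDP 1 − 0.75^(21/24) = 22.3%, CDS 1 − 0.75^(12/24) = 13.4%, odds ratio 1.85. With 354 per group and a simple two-proportion test that ignores centre effects, such a gap would reach significance about 87% of the time. Waits of 3 v 6 months give an odds ratio of 1.19, and equal waits give 1.00.

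**With an equal window from completion.** Over 12 months from completion, the same hazard gives 13.4% in both arms and the gap is zero.

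**Mid-episode transfers.** If onward referral during the index episode also counts, CFDP children are at risk from their first appointment, whereas CDS children are at risk only after leaving specialist care. The table leaves this out; it would add to the CFDP side.

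**The case against.** The strongest reply is that a clock from referral is a legitimate choice. It matches the primary outcome and the two-year horizon of the economic analysis, it gives both arms a common time zero, and it answers a service-load question that the rationale also raises. This stands, and it is why the count should be kept.

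The second reply concerns size. No wait is given for either arm. The quoted waits relate to GA treatment, the protocol adds that list numbers are falling, and a snapshot of children still waiting over-represents long waits. The children studied are those triaged as suitable for CFDP, with no or mild complexity. The rationale worries about return within a short time, and early returns are captured in both arms (Pattern B). This also stands. A reader might infer that the design builds in a bias of 5 to 14 points against CFDP; the documents do not support that.

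A reader might also infer that no return at all can occur during the wait and index treatment. That holds for the wait. It does not hold for CFDP treatment, because the research objectives expect onward referral from CFDPs and ask about it, for CFDPs only.

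Third, restarting the clock at discharge conditions on finishing the episode, which may itself differ by arm. This is a real cost, so the new analysis should be added and not substituted.

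Fourth, details of secondary outcomes often sit in the analysis plan. That is true of censoring rules, but here the protocol itself fixes the window and the model family.

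**Conclusion.** The point holds in limited form. Time since referral, analysed as a proportion without time at risk, gives a usable whole-pathway count but not a comparison of durability. If CDS waits are longer, the direction is fixed: with equal durability, CFDP shows more returns. The size cannot be derived from the documents. It is about 1 point or less when waits differ by a month, 1 to 2 points for CDS waits of 9 to 12 months if returns come early, and about 14 points for waits of 2 v 12 months with a constant 20% yearly hazard. The uneven event definition adds to this by an unknown amount.

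A reader might go further and conclude that the main answer of the study is compromised. It is not: this is one secondary outcome with no decision rule attached, and the primary questions concern GA and health economic impact.

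**What to change.** 1. Keep the two-year count from referral, label it a whole-pathway measure, and state that a difference in it will not be read as a difference in durability.
2. Add an analysis of new specialist referral after index treatment, as time to event with censoring at the end of available data. Start the clock at the initial appointment, whose date is on both the CDS and CFDP forms in Appendix B, or at completion where clinical or NHS BSA records give that date.
3. Report mid-episode transfers separately (CFDP to CDS or hospital; CDS to hospital), defined alike in both arms.
4. Show by arm the numbers never seen and the numbers not completing treatment.

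**Cost.** New outcome wording and one extra model. Neither arm's form lists a discharge date. The NHS BSA headings include completion and treatment-date fields, but they are requested for GDS and PDS contracts, so coverage of CDS care must be checked. Starting at the initial appointment is feasible in both arms but leaves any later wait, such as for a GA, inside the follow-up. The new analysis covers only children who were seen or who completed treatment, which is why item 4 must stand beside it.

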- *What are the health economic impacts of using CFDP?*
 - The study will identify and compare healthcare resource utilisation, and associated costs, of both pathways using data collected from HES, NHS BSA, and local clinical records.

Secondary

- *What are the long-term impacts of treatment in terms of antibiotic use, pain experienced, anxiety, further treatment required by CFDP compared to treatment through a traditional pathway?*
 - Using a text message questionnaire, data will be collected from parents/guardians regarding antibiotic use, pain experienced and anxiety of the patient.
- *What are dental teams' beliefs and views on CFDPs/traditional pathways?*
 - Using a qualitative methodology dental team views will be recorded and analysed.
- *Are patients satisfied with their experience in using CFDPs and traditional services?*
 - Patient experience will be recorded using an adapted version of the NHS Friends and Family Test recorded through a text message questionnaire.
- *Looking only at the CFDPs - what proportion require an onward referral and what characteristics necessitate an onward referral?*
 - The project will assess the characteristics of patients who do and do not require onward referral.
- *Does the scheme work differently across different localities, for different patients?*
 - The project will determine similarities and differences in how CFDP sites operate for the patients they see and treat.

II. INVESTIGATORS

Key Contacts

The Principal Investigator for this study will be:

[name]
University of Manchester
Dental Health Unit
[name]

Other individuals involved in this study include:

[name] [contact]
(University of Manchester; Statistician)

[name] [contact]
(University of Cambridge; Realist evaluation)

[name] [contact]
(University of Manchester)

[name] [contact]
(University of Liverpool; Consultant Dental Public Health)

[name] [contact]
(University of Manchester; Health Economist)

[name]
(Lay co-applicant / PPI advisor)

III. APPROVAL OF THE PROTOCOL

The protocol has been reviewed and approved in writing by NHS ethics (IRAS ID: 323977 REC Reference: 23/EM/0093), and The University of Manchester as sponsor.

The Principal Investigator will ensure all relevant staff participating in the study have appropriate training prior to study commencement.

IV. DURATION OF STUDY

3 Years (see timeline).

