- Secondary care resource use: dental extractions under GA. Data collected from routine data: HES and CDS software
- Intervention resource use for CFDP pathway: additional costs paid to deliver the pathway (as outlined in the service level agreement) and additional costs in terms of setting up the pathways (providing training and resources/support for dentists. Data collected from CFDP providers and commissioners.

Unit costs will be attached to dental treatments via the dental treatment band and the associated Units of Dental Activity cost. Unit costs for prescribed antibiotics will be obtained from Prescriptive Cost Analysis data (21). Unit costs for secondary care resource use are sourced from the Healthcare Resource Group tariffs for tooth extractions(22).

Intervention costs will be attached data from CFDP providers and commissioners using salary costs from Unit Costs of Health and Social Care (23). The cost per patient for each pathway will be summarised and presented adjusted for inflation.

The health economics analysis will adopt a cost-consequences approach whereby the costs of each pathway will be presented separately but alongside relevant outcomes: 1) dental extractions under GA, 2) count of children who are successfully seen and treated in each pathway, 3) count of treatments performed (extractions, restorations), 4) mean wait time and 5) dental pain experienced by a child. Resource use and costs from the CFDP pathway will also be used in a budget impact analysis. Differences in outcomes will be generated from the quantitative analysis.

The analysis will take an NHS perspective with a 2 year time horizon. Longer term costs and outcomes will not be modelled due to the need for treatment being acute and focusing on child teeth. This approach will provide dental service commissioners with appropriate health economic data to inform future commissioning decisions related to CFDP.

VII. Monitoring of the study

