Appendix A – Gantt Chart

APPENDIX B – Data collection

Data collected through CDS

ID	Contract Number	Provider Name	Locality	Month of Submission to Dental Comm Team	Practice patient code	Pt Age (in years)	Patient Postcode	URN	Referring Practice Name	Referring GDP Name	Referring Practice Postcode	Number of courses of Antibiotics whilst waiting?

Date of Referral	Appt made? (Yes / No)	Reason no appt (Please select from the drop down)	Number of appts attended	Number of appts WNB	Bitewings taken?	Date of Initial Appointment	Number of decayed teeth needing treatment *at CDS	Outcome (please select from drop down)

Treatment Provided								Notes	Who carried out treatment	Previously seen at CFDP or other services after referral	GM central emergency system (Out of hours) Y/N
Number of Filling(s)	Number of Extraction(s)	Number of Stainless Steel Crowns (SSCs)	Number of Temp Fillings	Fluoride Varnish Application (Y/N)	Silver Diamine Fluoride (SDF) (Y/N)	Oral Health Improvement Advice Given (Y/N)	Antibiotics (Yes / No)				

Data collected through CFDP

ID	Contract Number	Provider Name	Locality	Month of Submission to Dental Comm Team	Practice patient code	Pt Age (in years)	Patient Postcode	URN	Referring Practice Name	Referring GDP Name	Referring Practice Postcode

Number of courses of Antibiotics whilst waiting?	Date of Referral	Appt made? (Yes / No)	Reason no appt (Please select from the drop down)	Date of Initial Appointment	Number of appts attended	Number of appts WNB	Bitewings taken?	Number of decayed teeth needing treatment
			Cannot contact					

Treatment Provided								Outcome (please select from drop down)	Notes	Who carried out treatment	GM central emergency system (Out of hours) Y/N	Patie
Number of Filling(s)	Number of Extraction(s)	Number of Stainless Steel Crowns (SSCs)	Number of Temp Fillings	Fluoride Varnish Application (Y/N)	Silver Diamine Fluoride (SDF) (Y/N)	Oral Health Improvement Advice Given (Y/N)	Antibiotics (Yes / No)					

NHS BSA data headings

Link	Flagged (linked or not linked data set 0 = not linked, 1 = linked)
PANDA_ID	PANDA ID (include if linked)
PATIENT_ID	Patient ID (random number generated by NHS BSA for each patient)
Age of Pt at every CoT	age of Pt at every CoT (will need to use DOB and treatment date)
GENDER	Gender
PT_LSOA	Lower Super Output Area of patient's home address at time of treatment

IMD	UoM will supply this as a post-code lookup. IMD against NEPU 2019 scores an
IMD rank	

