Patient_charge_due	Patient charge due (££) for ever CoT
Patient_charge_collected	Patient charge actually collected (i.e. if they did not complete the course of treatment - are there outstanding payments owed? = remittance)
TX_COMPLETE	Is the treatment complete or incomplete? NO=0, Y=1
TX_DAYS	Interval in days between date of acceptance and date of completion or last visit
YEAR_MONTH	Date of when the form was submitted
TREATMENT_DATE	date of treatment
TREATMENT_CHARGE_BAND	treatment charge band
CONTRACT_TYPE	Type of contract (we are requesting information on: GDS / GDS and / PDS - no ortho needed).
12_MONTH_LIST	ND looking into this = Number of unique patients seen in previous 12 months (contract level)
24_MONTH_LIST	ND looking into this - Number of unique patients seen in previous 24 months (contract level)
PRACTICE_LSOA	Lower super output area of dental practice address
PRACTICE_CCG	Clinical commissioning group of dental practice address
PRACTICE_CCG_POPULATION_PER_DENTIST	Population per dentist of practice Clinical Commissioning Group
CONTRACT_UDAs	Annual number of contracted UDAs
CONTRACT_UDA_VAL	UDA Value (price per UDA)
CONTRACT_RADS_PER_100	Radiographs rate per 100 FP17s for contract (unless this is available by performer?)
CONTRACT_REATTEND	Average Re-attendance interval (days) on contract. I.e. number of days between courses of treatment completion and start of new course of treatment
FORM_ID	Is this just each treatment line - if so keep in
FOUNDATION_DENTIST	foundation dentist
AGE_LAST_3103	Dentists age. Age at that CoT (Age at march of that year - preceding treatment)
PERFORMER_NUMBER	NHS BSA to TRANSFORM into another numeric value to allow us to still identify the same performers within the dataset but not linkable to any real-world information
PERFORMER_PROVIDER	Is the performer also a provider (i.e. contract holder)? N=0, Y=1
PERFORMER_DATE_REGISTERED	Date of performer entry to General Dental Council register

PERFORMER_BDS_PLACE	Place of performer BDS qualification (from GDC / NHS Performers list)
PERFORMER_GENDER	
ADV_MAN_SERV	
ADV_MAN_SERV_COUNT1	YES "referral for advanced mandatory service"
ANTIBIOTICS	
ANTIBIOTICS_COUNT	
BEST_PRACTICE_COUNT	
CROWNS	
CROWNS_COUNT	
DECAYED_PERM	This is part of the DMFT index number of decayed teeth.
DECAYED_PERM_COUNT	This is part of the DMFT index if they completed the Decayed component. 0=N and 1=Y
ENDODONTIC_TREATMENT	
ENDODONTIC_TREATMENT_COUNT	
EXEMINATION_COUNT	
EXTRACT_ORTHO_COUNT	

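### The costing rule gives Community Dental Service care no unit cost of its own but adds delivery and set-up costs to the CFDP pathway, so a primary comparison probably understates comparator cost

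*Protocol*

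**What the plan says.** The Research objectives in section I of the protocol put "What are the health economic impacts of using CFDP" under the primary questions and add: "The study will identify and compare healthcare resource utilisation, and associated costs, of both pathways".

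The Cost effectiveness text in section VI sets out how this is done:

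- **Dental treatment, both pathways.** "Unit costs will be attached to dental treatments via the dental treatment band and the associated Units of Dental Activity cost". Antibiotics are priced separately, from prescription cost data.
- **Hospital care.** "Secondary care resource use: dental extractions under GA", priced at Healthcare Resource Group (HRG) tariffs for tooth extraction.
- **CFDP pathway only.** "Intervention resource use for CFDP pathway: additional costs paid to deliver the pathway", together with the cost of setting the pathway up (training, resources, support).

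The Background describes one of the two comparator settings as "dentists with enhanced skills and specialist equipment and facilities (Community Dental Service"). It also reports the criticism that the General Dental Services (GDS) contract does not allow for the extra time and resources that higher-need groups require. It explains the additional CFDP funding on the same ground.

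In Appendix B, treatment band and UDA value appear only in the NHS Business Services Authority (BSA) extract, whose contract field reads "Type of contract (we are requesting information on: GDS / GDS and / PDS - no ortho needed"). The CDS and CFDP forms both record appointments attended and "GM central emergency system (Out of hours) Y/N".

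**The concern.** The protocol treats the UDA price as too low for these children when they are seen in a CFDP, and it adds the extra payments there. It makes no matching addition when similar children are seen in the CDS, a service that it describes as better equipped and more specialised. If CDS delivery costs more than its UDA price, the comparator looks too cheap.

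The concern that the study is meant to test, stated in the rationale, is that the scheme could end up costing more than usual care. A costing rule that leans towards that answer before any data arrive weakens a primary result and the budget impact analysis that follows from it.

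**Working it through.** The protocol states no unit cost and no cost difference, so there is no figure to reproduce. The check has two parts: the cost lines side by side, then an illustration with assumed values.

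**Cost lines as written (section VI, Cost effectiveness)**

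| Item | CFDP | Comparator |
|---|---|---|
| Non-GA dental treatment | band × UDA cost | band × UDA cost |
| Antibiotics | yes | yes |
| GA extraction | HRG tariff | HRG tariff |
| Delivery payments and set-up | yes | none |
| Specialist delivery cost of the CDS | – | none |
| Assessment visits; hospital care other than GA extraction | no line | no line |
| Out-of-hours use | recorded, no line | recorded, no line |

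For identical non-GA treatment the rule makes a CFDP course dearer by the whole CFDP addition, whatever CDS care really costs.

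**Illustration, in units of one UDA-priced course**

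Inputs:
- GA proportions of 25% (comparator) and 15% (CFDP), from Sample size in section V.
- *e*, CFDP addition per child; *G*, cost of one GA; *s*, share of CFDP children referred on to the CDS; *m*, true CDS cost relative to its UDA price. All four are assumptions.
- Each child has one non-GA course in the pathway entered.

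Difference (CFDP minus comparator) under the planned rule:
(1 + e + s + 0.15G) − (1 + 0.25G) = e + s − 0.10G

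Difference with CDS care at its own cost:
(1 + e + s·m + 0.15G) − (m + 0.25G) = 1 + e + s·m − m − 0.10G

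Planned minus corrected:
s − s·m + m − 1 = **(m − 1)(1 − s)**

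The terms *e* and *G* cancel, so the tilt depends only on *m* and *s*:

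| m | s = 0 | s = 0.3 |
|---|---|---|
| 1.00 | 0 | 0 |
| 1.25 | 0.25 | 0.175 |
| 1.50 | 0.50 | 0.35 |
| 2.00 | 1.00 | 0.70 |

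Referral onward shrinks the tilt because those CFDP children's CDS care is under-priced too.

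If only the 75% of comparator children without a GA have a non-GA CDS course, the factor (1 − s) becomes (0.75 − s). The range is then 0.25 × (0.75 − 0.3) = 0.1125 to 1.0 × 0.75 = 0.75.

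**Can the sign change?** It can, but it need not. Take e = 0.5, s = 0.3, m = 1.5.
- G = 5: planned 0.5 + 0.3 − 0.5 = +0.30; corrected 1 + 0.5 + 0.45 − 1.5 − 0.5 = −0.05. The sign reverses.
- G = 10: planned 0.5 + 0.3 − 1.0 = −0.20; corrected 1 + 0.5 + 0.45 − 1.5 − 1.0 = −0.55. The sign stays.

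**The case against.** The strongest reply is that the direction is inferred. The protocol gives no CDS cost and does not say what contract the CDS holds. Both data forms carry a contract number, and the BSA extract asks for a UDA value by contract, so a CDS-specific UDA price may be intended. That possibility stands. It would bring *m* nearer to 1, but the protocol does not say so.

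A second reply is that unit-cost sources belong in a later analysis plan. That would hold if the protocol were silent, but it states the rule itself, and states it unequally. Counting set-up costs for a new service and not for an established one is a defensible incremental choice. It does not settle how CDS delivery is priced.

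Several stronger readings are tempting, and the protocol does not support them:

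- *The CFDP can look cheaper only by avoiding GAs.* Antibiotics and all treatments are costed in both pathways, so fewer prescriptions, fewer courses or lower bands could also offset the addition.
- *The budget impact excludes comparator costs.* The text says that CFDP resource use and costs will be used in it. It does not say that nothing else will be.
- *The CDS form is deficient because it has no treatment band.* The CFDP form has none either.
- *Assessment before a GA is certainly uncosted.* That depends on what the HRG tariff covers, which cannot be checked here.
- *The cost result alone decides the scheme's future.* Section I ties that decision to the project as a whole. The analysis is cost-consequences: costs are shown beside five outcomes, with no cost decision rule.

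**Conclusion.** The point holds in a limited form. As written, the costing rule probably understates comparator cost in a primary comparison, because CDS care carries no delivery cost beyond the UDA price while CFDP care does.

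The direction rests on CDS care costing more than its UDA price. The protocol's description of the CDS and its account of the GDS contract support this but do not state it. The size is unknown. Under the assumed ranges (m from 1.25 to 2.0, s from 0 to 0.3) it is 0.175 to 1.0 UDA-priced course per child, and it is zero at m = 1. Whether the conclusion would change depends on unit costs that the protocol does not give.

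The primary GA outcome and its sample size are not affected.

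**What to change.** Amend the Cost effectiveness text in section VI, and the matching paragraph in section X, as follows:

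1. Cost non-GA CDS attendances with a CDS-specific unit cost, for example commissioner contract value divided by activity, or the salary-based source already cited for CFDP costs. Use the number of appointments attended on the CDS form as the volume.
2. Apply the same unit cost to CFDP children referred on to the CDS, and say where their attendance counts come from.
3. In both arms, cost hospital and CDS assessment visits that the HRG tariff does not already cover, and recorded out-of-hours use. The latter is a yes/no field, so state the number of contacts assumed for each yes.
4. State that the budget impact uses the net difference between pathways.
5. Vary the CDS unit cost over a stated range in a sensitivity analysis.

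The cost is a wording change and one further request to commissioners, who already supply CFDP costs. The drawback is that CDS costs will be averages and not patient-level figures, which is why the sensitivity range is needed.
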